Department of Clinical Epidemiology Aarhus University and Aarhus University Hospital DENMARK

Bordeaux PharmacoEpi, Université de Bordeaux FRANCE

Centre for Pharmacoepidemiology Karolinska Institutet SWEDEN

NON-INTERVENTIONAL STUDY (NIS) PROTOCOL

PASS information

[
Title	A Drug Utilization Study to Evaluate the
	Effectiveness of Risk Minimization
	Measures (RMMs) for Abrocitinib in the EU
	Using Electronic Healthcare Data
Protocol number	B7451085
Protocol version identifier	2.0
Date	23 May 2024
EU Post Authorization Study (PAS)	To be registered before the start of data
register number	collection
Active substance	Abrocitinib (PF-04965842)
	Anatomical Therapeutic Chemical (ATC)
	code D11AH08
Medicinal product	Cibinqo
Product reference	EU/1/21/1593/001; EU/1/21/1593/002;
	EU/1/21/1593/003; EU/1/21/1593/004;
	EU/1/21/1593/005; EU/1/21/1593/006;
	EU/1/21/1593/007; EU/1/21/1593/008;
	EU/1/21/1593/009; EU/1/21/1593/010;
	EU/1/21/1593/011; EU/1/21/1593/012;
	EU/1/21/1593/013; EU/1/21/1593/014;
	EU/1/21/1593/015.
Procedure number	EMEA/H/C/005452/0000
Marketing Authorization Holder(s)	Pfizer Europe MA EEIG
(MAH)	[name]
	Brussels, 1050
	Belgium
Joint PASS	No
Research objective	The study objectives are to evaluate, to the
	extent measurable in the available routinely collected data, indicators of healthcare

PFIZER CONFIDENTIAL

Version 2.0, 25 May 2024	
	professional's (HCP) adherence to the RMMs in accordance with the abrocitinib Summary of Product Characteristics (SmPC) and prescriber's brochure, specifically:
	 indicators of adherence to performing laboratory tests of complete blood count (CBC), lipid panel, hepatitis B/C and tuberculosis (TB) screening prior to initiation of abrocitinib treatment,
	• indicators of adherence to performing laboratory tests of CBC and lipid panel at week 4 (± 2 weeks) after initiation of abrocitinib treatment,
	 indicators of adherence to consideration of risk factors for venous thromboembolism (VTE), major adverse cardiovascular event (MACE), malignancy (excluding non-melanoma skin cancer [NMSC]), NMSC, and serious infection prior to initiation of abrocitinib treatment,
	• indicators of adherence to avoid live attenuated vaccine immediately prior to and during treatment with abrocitinib,
	• indicators of adherence to contraindications for use during pregnancy,
	• indicators of adherence to contraindications for use among patients with severe hepatic impairment,
	• indicators of adherence to no use in patients aged <12 years, and

	• indicators of adherence to recommended posology (estimated average daily dose)
Country(-ies) of study	Denmark, France, Sweden, Spain, and Hungary
Author	[name], MPH, DSc
	Department of Clinical Epidemiology,
	Aarhus University, Aarhus, Denmark

Marketing Authorization Holder(s)

Marketing Authorization Holder(s)	Pfizer Europe MA EEIG
	[name]
	Brussels
	1050
	Belgium
MAH contact person	[name], MSc
	Safety Surveillance Research Scientist
	Worldwide Safety
	Pfizer, Inc.
	[name]
	New York, NY 10001

This document contains confidential information belonging to Pfizer. Except as otherwise agreed to in writing, by accepting or reviewing this document, you agree to hold this information in confidence and not copy or disclose it to others (except where required by applicable law) or use it for unauthorized purposes. In the event of any actual or suspected breach of this obligation, Pfizer must be promptly notified.

Abrocitinib B7451085 NON-INTERVENTIONAL STUDY PROTOCOL Version 2.0, 23 May 2024 1. TABLE OF CONTENTS	
1. TABLE OF CONTENTS	5
2. LIST OF ABBREVIATIONS	7
3. RESPONSIBLE PARTIES	9
4. ABSTRACT	11
5. AMENDMENTS AND UPDATES	13
6. MILESTONES	14
7. RATIONALE AND BACKGROUND	15
8. RESEARCH QUESTION AND OBJECTIVES	17
8.1. Research question	17
8.2. Research objectives	17
9. RESEARCH METHODS	17
9.1. Study design	17
9.2. Setting	17
9.2.1. Inclusion criteria	18
9.2.2. Exclusion criteria	18
9.3. Variables	18
9.4. Data sources	25
9.5. Study size	27
9.6. Data management	28
9.7. Data Analysis	29
9.7.1. Main analyses	29
9.7.2. Sensitivity analyses	31
9.8. Quality Control	31
9.9. Limitations of the Research Methods	32
9.10. Other aspects	32
10. PROTECTION OF HUMAN SUBJECTS	32
10.1. Patient information	32
10.2. Patient consent	33
10.3. Institutional Review Board (IRB)/Independent Ethics Committee (IEC)	33
10.4. Ethical conduct of the study	33

PFIZER CONFIDENTIAL

abrocitinib	
37451085 NON-INTERVENTIONAL STUDY PROTOCOL	
Version 2.0, 23 May 2024	

2. LIST OF ABBREVIATIONS

Abbreviation	Definition		
AD	Atopic Dermatitis		
AE	Adverse Event		
aRMM	Additional Risk Minimization Measure		
ATC	Anatomical Therapeutic Chemical		
CBC	Complete Blood Count		
CCAM	Classification Commune des Actes Médicaux		
CI	Confidence Interval		
CIOMS	Council for International Organizations of Medical Sciences		
CIP	Code Identifiant de Présentation		
CPR	Central Person Registration		
DHPC	Direct healthcare professional communication		
EMA	European Medicines Agency		
ENCePP	European Network of Centres for Pharmacoepidemiology and		
	Pharmacovigilance		
EU	European Union		
FDA	Food and Drug Administration		
GPP	Good Pharmacoepidemiology Practice		
GVP	Good Pharmacovigilance Practice		
НСР	Healthcare Professional		
HDL	High-Density Lipoprotein		
ICD	International Classification of Diseases		
IEC	Independent Ethics Committee		
IL	Interleukin		
IQR	Interquartile Range		
IRB	Institutional Review Board		
ISPE	International Society for Pharmacoepidemiology		
JAK	Janus Kinase		
LDL	Low-Density Lipoprotein		
MACE	Major Adverse Cardiovascular Event		
MAH	Marketing Authorization Holder		
NABM	Nomenclature des Actes de Biologie Médicale		
NHIFA	National Insurance Fund Administration		
NIS	Non-Interventional Study		
NOMESCO	Nordic Medico-Statistical Committee		
NPU	Nomenclature, Properties and Units		
PASS	Post-Authorization Safety Study		
RMM	Risk Minimization Measures		
SAP	Statistical Analysis Plan		
SIDIAP	The Information System for Research in Primary Care		
SmPC	Summary of Product Characteristics		

Abbreviation	Definition	
SNDS	Système National des Données de Santé (French Administrative	
	Healthcare Database)	
TB	Tuberculosis	
TG	Triglycerides	
UCD	Unité Commune de Dispensation	
VTE	Venous Thromboembolism	
WHO	World Health Organization	

4. ABSTRACT

Title A Drug Utilization Study to Evaluate the Effectiveness of RMMs for Abrocitinib in the EU Using Electronic Healthcare Data.

Protocol B7451085; Version 2.0; 23 May 2024

Main author: [name], Aarhus University, on behalf of the SIGMA Research Team

Rationale and background Atopic dermatitis (AD) is the most common chronic inflammatory skin disease. Abrocitinib received marketing authorization for the European Union (EU) on 09 December 2021 and is indicated for the treatment of moderate to severe AD in adults and adolescents 12 years and older who are candidates for systemic therapy. To mitigate the risks associated with abrocitinib, required routine RMMs including the SmPC and package leaflet are being employed. In addition to the routine risk minimization measures, additional risk minimization measures (aRMMs) including a prescriber's brochure and patient card, are being implemented in the EU.

Research question and objectives The study objectives are to evaluate, to the extent measurable in the available routinely collected data, indicators of HCPs' adherence to the RMMs in accordance with the abrocitinib SmPC and prescriber's brochure, as measured by:

- indicators of adherence to performing laboratory tests of CBC, lipid panel, hepatitis B/C, and TB screening prior to initiation of abrocitinib treatment,
- indicators of adherence to performing laboratory tests of CBC and lipid panel at week 4 (± 2 weeks) after initiation of abrocitinib treatment,
- indicators of adherence to consideration of risk factors for VTE, MACE, malignancy excluding NMSC, NMSC, and serious infection prior to treatment with abrocitinib,
- indicators of adherence to avoid live attenuated vaccines immediately prior to and during treatment with abrocitinib,
- indicators of adherence to contraindications for use during pregnancy,
- indicators of adherence to contraindications for use among patients with severe hepatic impairment
- indicators of adherence to no use in patients aged < 12 years, and
- indicators of adherence to recommended posology (estimated average daily dose).

Study design This will be a descriptive drug utilization study using secondary data from healthcare databases in Denmark, France, Sweden, Spain and Hungary.

Population The study population will include patients with a dispensing of abrocitinib as recorded in routinely collected electronic healthcare data in Denmark, France, Sweden, Spain and Hungary during the study period (study start: country-specific aRMM distribution [01

PFIZER CONFIDENTIAL

Abrocitinib B7451085 NON-INTERVENTIONAL STUDY PROTOCOL Version 2.0, 23 May 2024 March 2022, Sweden; 09 March 2022, Denmark; 31 July 2022, France; 30 Jan 2023, Spain; 05 April 2024, Hungary]; study end: December 2026). These countries have universal healthcare.

Variables The study will collect all relevant data including patient demographics, comorbidities, prescription medications, vaccine administration, and laboratory testing prior to the initiation of abrocitinib and during treatment with abrocitinib to address the study objectives.

Data sources This study will utilize routinely collected electronic healthcare data from national or regional population-based electronic healthcare registers in Denmark, Sweden, and Spain and an administrative healthcare databases in France and Hungary.

Study size All patients initiating abrocitinib during the study period will be included.

Data analysis Data will be analysed in each country separately using a common protocol, database-specific definitions of the study variable, and common analysis strategy. The main indicators will be proportions of abrocitinib users with a given indicator of aRMM adherence.

Milestones

Milestone	Planned date*
Registration in the HMA-EMA Catalogues of RWD Studies	To be registered before the start of data collection
Start of data collection	31 December 2024
End of data collection (the date from which the analytical dataset is completely available, i.e., clean and coded data from all participating countries/databases)	15 May 2028
Interim Report 1	15 November 2025
Interim Report 2	15 May 2027
Final study report	15 November 2028

* Subject to data delivery and application approval timelines by data custodians in participating countries

5. AMENDMENTS AND UPDATES

Amendment number, date	Section	Amendment	Rationale
1.0, 23 May 2024	PASS information; Section 4; Section 8.2; Section 9.7.1	Replaced <18 with <12 as the cut-off for off-label use	< 12 is the correct age for off-label use consistent with adolescent indication (12 years and older) in the EMA
1.0, 23 May 2024	PASS information; Section 4; Section 8.2; Table 2; Section 9.7.1	Separated 'malignancy' into: • malignancy excluding NMSC • NMSC	Consistency with EU RMP important potential risks (v 4.2) published subsequent to V 1.0 B7451085 study protocol
1.0, 23 May 2024	Section 4; Section 7	Include adolescent indication, date of adolescent authorization in the EU, and update the list of potential risks	Consistency with EU RMP updates (v 4.2) published subsequent to V 1.0 B7451085 study protocol
1.0, 23 May 2024	Section 6, Section 12, Annex 2	References to EU PAS Register replaced with HMA- EMA Catalogues of RWD Studies (note, references to 'EU PAS Register Number' remain	Administrative update to reflect changes implemented to EU PAS registration system subsequent to V 1.0 B7451085 study protocol
1.0, 23 May 2024	Section 4, Section 9.2, Section 9.2.1	Updated date of aRMM distribution for Hungary	Data on actual aRMM distribution date, rather than estimated, became available

6. MILESTONES

Milestone	Planned date*
Registration in the HMA-EMA Catalogues of RWD Studies	To be registered before the start of data collection
Start of data collection	31 December 2024
End of data collection (the date from which the analytical dataset is completely available, i.e., clean and coded data from all participating countries/databases)	15 May 2028
Interim Report 1	15 November 2025
Interim Report 2	15 May 2027
Final study report	15 November 2028

* Subject to data delivery and application approval timelines by data custodians in participating countries

7. RATIONALE AND BACKGROUND

AD, also known as atopic eczema, is the most common chronic inflammatory skin disease. AD is characterized by intense itching and recurrent eczematous lesions (1). AD was originally thought to affect primarily preschool children, with prevalence up to 25%, but recent evidence shows that AD in adults has an estimated prevalence of 7–10% (2). AD has a strong genetic component, is associated with atopic co-morbidities including asthma, allergic rhinitis, and food allergies, and coincides with an increased risk of other inflammatory diseases, such as arthritis and inflammatory bowel disease. AD confers a substantial burden to patients and their families, resulting in high healthcare costs. AD has been linked to psychological disturbances and reduced educational attainment (2, 3). Severe and active AD is associated with an increased risk of cardiovascular morbidity (4-6) and with certain types of malignancies (7).

Abrocitinib is a selective Janus Kinase (JAK) 1 inhibitor. The inhibition of JAK1 is thought to modulate multiple cytokines involved in the pathophysiology of AD including interleukin (IL)-4, IL-13, IL-31, IL-22, and interferon gamma. The important identified and potential risks were adopted based on non-clinical and clinical data from abrocitinib development program and from understanding of data from other JAK inhibitors (i.e., tofacitinib, baricitinib, upadacitinib). The important identified risks include VTE and herpes zoster. The important potential risks include serious and opportunistic infections, malignancy major adverse cardiovascular event (MACE), myopathy (including rhabdomyolysis), gastrointestinal perforation, and impaired bone growth and development in patients in patients aged <12 years if used off-label, and fractures. (8). Finally, embryofetal toxicity following exposure in utero is included as a potential risk. Although abrocitinib is contraindicated for use in pregnancy, the patient population will include women of childbearing potential and off-label incidental/unintended exposure during pregnancy could occur (8). Abrocitinib received marketing authorization for EU on 09 December 2021 for the treatment of moderate to severe AD in adults who are candidates for systemic therapy (8). On 21 March 2024, the indication for abrocitinib marketing authorization for the EU was expanded to adolescents 12 years and older.

To mitigate the risks associated with abrocitinib, required routine RMMs including the SmPC and package leaflet are being employed (8). In addition to the routine RMMs, aRMMs are being implemented in the EU. The aRMMs include an educational program intended to enhance the communication of the risks and risk minimization practices to HCPs via a "Prescriber's Brochure", a one-time direct healthcare professional communication (DHPC) and to patients via a patient card. The overall objective of the aRMM is to provide appropriate tools designed to enhance the awareness and knowledge of HCPs and patients about the safety risks and to ensure the optimal use of abrocitinib.

A systematic evaluation of the effectiveness of RMMs helps to understand whether the program objectives have been met or provide evidence that further amendments to the program are needed. This protocol describes the objectives and methods used to assess the effectiveness of the RMMs for abrocitinib in five EU countries: Denmark, France, Sweden, Spain and Hungary (9).

This non-interventional study (NIS) is designated as a Post-Authorisation Safety Study (PASS) and is a commitment to the European Medicines Agency (EMA).

8. RESEARCH QUESTION AND OBJECTIVES

8.1. Research question

Does routinely collected data in the EU indicate adherence to the recommendations for use of abrocitinib described in SmPC, prescriber's brochure and DHPC?

8.2. Research objectives

The study objectives are to evaluate, to the extent measurable in the available routinely collected data, indicators of HCPs' adherence to the RMMs in accordance with the abrocitinib SmPC, prescriber's brochure and DHPC, specifically:

- Indicators of adherence to performing laboratory tests of CBC, lipid panel, hepatitis B/C and TB screening prior to initiation of abrocitinib treatment,
- Indicators of adherence to performing laboratory tests of CBC and lipid panel at week 4 (± 2 week) after initiation of abrocitinib treatment,
- Indicators of adherence to consideration of risk factors for VTE, MACE, malignancy excluding NMSC, NMSC, and serious infection prior to treatment with abrocitinib,
- Indicators of adherence to avoid live attenuated vaccines immediately prior to and during treatment with abrocitinib,
- Indicators of adherence to contraindications for use during pregnancy,
- Indicators of adherence to contraindications for use among patients with severe hepatic impairment,
- Indicators of adherence to no use in patients aged < 12 years, and
- Indicators of adherence to recommended posology (estimated average daily dose).

9. RESEARCH METHODS

9.1. Study design

This will be a descriptive drug utilization study using secondary data from healthcare databases in Denmark, France, Sweden, Spain and Hungary. The study population will comprise patients who are treated with abrocitinib.

9.2. Setting

The study population will include patients with a dispensing of abrocitinib as recorded in routinely collected electronic secondary population data in Denmark, France, Sweden, Spain and Hungary between the study start (country-specific aRMM distribution [01 Mar 2022, Sweden; 09 Mar 2022, Denmark; 31 Jul 2022, France; 30 Jan 2023, Spain; 05 April 2024, Hungary]) and study end (December 2026). Details on the data sources are in Section 9.4). All participating countries have universal health care.

9.2.1. Inclusion criteria

All patients with at least 1 dispensing of abrocitinib between study start (country-specific aRMM distribution [01 Mar 2022, Sweden; 09 Mar 2022, Denmark; 31 Jul 2022, France; 30 Jan 2023, Spain; 05 April 2024, Hungary]) and December 2026 in the participating databases will be eligible for inclusion in this study. The date of the first dispensing of abrocitinib will be the index date. Patients must meet the above inclusion criteria to be eligible for inclusion in the study.

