9.2.2. Exclusion criteria

There are no exclusion criteria in this study.

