Hungary: Hungary has a single-payer healthcare system with a purchaser-provider split model and output-based payment system. The National Insurance Fund Administration (NHIFA) database contains information on healthcare covered by the state for over 9 million people in Hungary, and has national coverage for reimbursed services (medicine, out- and inpatient services) (31). Data are available for retrospective analyses from 01 January 2004. The NHIFA database includes information on demographics, mortality, Abrocitinib

B7451085 NON-INTERVENTIONAL STUDY PROTOCOL Version 2.0, 23 May 2024

prescribed drug codes, inpatient diagnostic and procedural codes, and outpatient lab, diagnostic services, and diagnostic codes.

There are four NHIFA registers: Demography, Drugs, Inpatient, and Outpatient. The Demography register includes sex, age, and date of death. The Drugs register captures brand information, date, ATC7 codes, volume, ICD codes, and territory. Further, information is collected regarding EU number, invented name, strength, pharmaceutical form, route of administration, packaging, and content. The Inpatient register comprises date (admission, discharge, and length of stay), location, ICD codes, Diagnosis Related Groups (DRG), and International Classification of Procedures in Medicine (ICPM) codes. The Outpatient register captures labs and diagnostic services and specialist visits, including date, location, ICD codes, and ICPM codes.

The research centres affiliated with this study and the associated data sources from Denmark, Sweden, France and Spain are listed in the European Network of Centres for Pharmacoepidemiology and Pharmacovigilance (ENCePP) Register (https://www.encepp.eu/encepp/viewResource.htm?id=42185, https://www.encepp.eu/encepp/viewResource.htm?id=42187, https://www.encepp.eu/encepp/viewResource.htm?id=2291, https://www.encepp.eu/encepp/viewResource.htm?id=41070, https://www.encepp.eu/encepp/viewResource.htm?id=38744)

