9.9. Limitations of the Research Methods

Given the use of data sources from 5 distinct EU countries in this study, there will be variability in data captured across the participating countries. For example, data on laboratory tests and vaccinations are not available in Sweden and may be underrecorded in Denmark and France. If only reimbursed services are recorded (e.g., vaccinations, oral contraceptives), some underascertainment will be associated with absence of data on nonreimbursed services. Given the underrecording, absence of a record of a given RMM metric (e.g., hepatitis B, hepatitis C, or TB screening) cannot be interpreted as an indicator of nonadherence for all metrics, and only databases with high completeness of these data should be used in that assessment (Table 2). Similarly, as vaccines recording is based on reimbursement and data is not expected to be complete, the absence of a record is not necessarily indicative of absence of vaccine receipt. Additionally, prescription strength data serves as a proxy for daily dosage in this study; this approach is supported by the absence of scoring on the abrocitinib 200 mg tablets (which would facilitate splitting into separate 100 mg doses), and by reimbursement in Sweden, Denmark, France and Spain (pending for Hungary) for both the 100 mg and 200 mg tablets (i.e. there is no financial justification for a patient to receive a prescription strength of 100 mg to be taken as 2 tablets to achieve 200 mg daily dosage). However, there may be instances where patient dosage does not correspond to the strength prescribed. Dosage data from SIDIAP can only be derived from a combination of WHO Defined Daily Dose (DDD); data from NHIFA on dosage is not available.

Other limitations include uncertainty about identification of abrocitinib in Denmark (however, most newly approved medicines receive hospital procedure codes); incomplete identification of ongoing pregnancies and pregnancies ending in a termination, as they are identifiable only by pregnancy end date; challenges in identifying screening for TB and hepatitis B and C in all participating countries; and potential underestimation of history of atherosclerotic disease given the likelihood of treatment within a primary care setting in all participating countries. Results from participating countries will not necessarily be generalizable to other countries in the EU.

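### Inclusion rule and index date have no new-user condition, contradicting the abstract and leaving earlier starters indexed on a refill or on a pre-aRMM date

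*Protocol*

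**What the plan says.** Section 9.2.1 makes eligible "All patients with at least 1 dispensing of abrocitinib between study start" and December 2026. Study start is the national aRMM distribution date: "01 Mar 2022, Sweden; 09 Mar 2022, Denmark; 31 Jul 2022, France; 30 Jan 2023, Spain; 05 April 2024, Hungary". The same section adds "The date of the first dispensing of abrocitinib will be the index date". Section 9.2.2 reads "There are no exclusion criteria in this study", and no washout or prior-use rule appears elsewhere in the protocol.

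The abstract, under study size, describes a narrower population: "All patients initiating abrocitinib during the study period will be included".

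Four of the eight items in Section 9.7.1 depend on when treatment began:
- Item 1: laboratory tests and screening in the 3 months before initiation.
- Item 2: CBC and lipids at week 4 (± 2 weeks) after initiation.
- Item 3: risk factors in the 6 months before initiation.
- Item 8: starting dose and duration of use.

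On timing, Section 7 states "Abrocitinib received marketing authorization for EU on 09 December 2021". Section 9.7.2 adds a sensitivity analysis with study start moved back to that date.

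**The concern.** Patients with any dispensing in a window and patients who initiate in that window are different populations. The operative criteria carry the wider one, while the abstract and the initiation-anchored indicators need the narrower one. The drug could lawfully be dispensed before every country's study start, so a patient who began in the gap and refilled afterwards qualifies.

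Such a patient has no satisfactory index date under the text as it stands. If first means first in the period, a refill is treated as initiation. If it means first ever, the prescribing decision predates distribution of the additional materials that define study start.

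At stake are the proportions for items 1, 2, 3 and 8. There is also a consistency risk: each country is analysed separately under a common protocol, and centres could resolve the ambiguity differently.

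**Working it through.** **Gap from authorisation to study start.** Dates are from Sections 7 and 9.2.1, laboratory availability from Table 2. From 09 December 2021 to 31 December 2026 is 1,848 days.

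| Country | Gap (days) | Gap / 1,848 | Item 1 and 2 tests available |
|---|---|---|---|
| Sweden | 82 | 4.4% | none |
| Denmark | 90 | 4.9% | CBC, lipids (hospital) |
| France | 234 | 12.7% | CBC, lipids, TB, hepatitis B/C |
| Spain | 417 | 22.6% | CBC, lipids (primary care) |
| Hungary | 848 | 45.9% | CBC, lipids, TB, hepatitis B/C |

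The third column would equal the share of earlier starters only if uptake were even from the day of authorisation and every gap starter refilled after study start. Neither is documented, so it is a rough guide. A later national launch or rising uptake makes the share smaller. The Hungarian figure is not usable, for the reason given in the objection.

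**Reading A: first dispensing in the period.** The index is a refill. Three months is about 90 days, so once more than about 90 days separate true initiation from that refill, the whole item 1 window lies on treatment. Baseline TB or hepatitis screening that was properly done then falls outside it. The week-4 window follows a refill, the starting dose is a continuing dose, and duration of use loses its beginning.

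**Reading B: first dispensing ever.** All windows are correctly placed, but some index dates precede study start. That conflicts with the abstract's condition that initiation falls in the study period.

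**Illustrative size under Reading A.** Reported proportion = p₁(1 − s) + p₂s, with s the share of earlier starters, p₁ the tested proportion in true initiators and p₂ that in refill windows. All three inputs are assumptions.
- p₁ = 0.80, p₂ = 0.30: s = 5% gives 77.5%, s = 10% gives 75%, s = 12.7% gives 0.80 − 0.50 × 0.127 = 73.7%.
- p₁ = 0.80, p₂ = 0.40: s = 5% gives 78%, s = 10% gives 76%, s = 20% gives 72%.
- s = 0 gives 80%, with no bias.

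**Against the planned precision.** Section 9.5: n = 0.5 × 0.5 × 1.959964² / 0.05² = 384.15, rounded up to 385, which reproduces the protocol's figure. A new-user rule does not enter this formula. In the first scenario, s = 10% shifts the estimate by 5 points, equal to the planned half-width. Adding patients does not reduce that shift.

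**Can prior use be checked?** Section 9.3 caps lookback at 365 days for characteristics. Borrowed for prior use, that is shorter than the gaps in Spain (417) and Hungary (848). Longer history exists: Section 9.4 gives drug data from 2005 in Sweden, records from 2006 in SIDIAP and data from 2004 in Hungary.

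**The case against.** The best reply is that new-user intent is visible: the abstract says initiating, the items refer to initiation and starting dose, and the natural sense of first dispensing is the one that starts treatment. This stands as evidence of intent. It does not amend 9.2.1 and 9.2.2, which are the operative text and state the wider rule.

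Second, the two harms are alternatives. A reader might infer that both occur together; they cannot for the same patient. Under Reading B only timing relative to the aRMM remains. Even that is partial, since the research question in Section 8.1 also covers the SmPC, which Section 9.7.2 dates to 09 December 2021.

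Third, the sensitivity analysis from that date removes refill indexing, because the first dispensing since authorisation becomes the index. That is correct for the sensitivity analysis. It mixes pre-aRMM starters with the rest and leaves the main analysis unchanged.

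Fourth, a reader might take Hungary's 848 days as the largest problem, or expect depressed TB and hepatitis screening everywhere. The protocol does not support either. Table 2 offers those screenings only in France and Hungary. The Hungarian database covers reimbursed services, and Section 9.9 describes reimbursement as "pending for Hungary", so fills before study start are probably unrecorded. Sweden has no laboratory data, so items 1 and 2 do not arise there, and Hungary has no dose data for item 8. For CBC and lipids the direction is uncertain, since on-treatment monitoring could place tests in the window.

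Finally, operational algorithms are deferred to the SAP. Eligibility and index date are not among them; Section 9.2 fixes both.

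**Conclusion.** The concern holds as an internal contradiction with a potential bias of unknown size. Sections 9.2.1 and 9.2.2, applied as written, admit patients who were already on treatment and give them either a refill date or a pre-aRMM date. The abstract and items 1, 2, 3 and 8 presuppose neither.

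It would go too far to say that the main results will be materially biased. The gaps of 82 to 848 days are facts, but they run from EU authorisation and not from national launch. The protocol gives no launch dates and no counts of pre-start users, and the effect is nil in any country without earlier dispensing. The 72% to 78% illustrations rest wholly on assumed shares and test probabilities. Any TB and hepatitis effect is confined to France and possibly Hungary.

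The correction still belongs in the protocol, because the index date is fixed there, it anchors half of the planned items, and putting it right costs very little. A before/after comparison is not required: Section 9.5 rules out comparative analyses.

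**What to change.** In Section 9.2.1, define the index date as the first-ever recorded abrocitinib dispensing, with prior use checked on all available history back to at least 09 December 2021. For items 1, 2, 3 and 8, require that date to fall on or after the country's study start. Keep patients with earlier dispensings as a separately reported group for items 4 to 7. They should stay in item 7, so that any use below age 12 is still counted. Align the abstract and Sections 9.2, 9.2.1 and 9.2.2 with this wording.

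Add to Section 9.9 that unreimbursed prior use in Hungary is not visible, so a first recorded fill there may not be true initiation. Optionally, show pre-aRMM initiators in their own descriptive column in the Section 9.7.2 analysis.

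The cost is about one eligibility sentence, matching edits elsewhere and a slightly smaller denominator for the initiation indicators. The required 385 is unchanged.
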